### **Intervention and comparison**

SIESTA is based on a CBT sleep intervention for typically developing adolescents and a CBT intervention focused on motivational planning for adolescents with ADHD, both developed by (amongst others) the project applicants.[36,37] The training follows a structured workbook for the adolescent which can be used during sessions and at home.[24] The instructions for the therapist are described in a therapist manual.[25] SIESTA consists of seven individual sessions with the adolescents, and two parental sessions. An overview of the content of the sessions can be found in Table 2. This RCT uses as control condition TAU for ADHD symptomatology. In Flanders TAU for ADHD primarily consists of medication with stimulants.

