### **Outcome measures**

#### **Primary outcomes**

**Objective sleep architecture: TST, SOL, SE, and NoA.** Sleep is registered with wrist actigraphy (Motionwatch, CamNtech Ltd) as objective measurement. Participants wear an actigraph for five school nights and two weekend nights, as based on previous research,[38] this is sufficient to be able to compute reliable sleep architecture estimates. Actigraphy has been reliably used in adolescents with sleep problems and has been shown to be sensitive to treatment effects.[13,38,39] Participants use the event marker button on the actigraph to indicate lights out and getup times.[40] If they forget to press the button, those time points are extracted from the sleep diary data. Using this data, TST (time asleep between sleep onset and sleep offset), SOL (time from lights out to sleep onset), and SE (percentage of time spent asleep TST while in bed TiB), and NoA (number of times awake after sleep onset and before sleep offset) are calculated.

**Subjective sleep architecture.** Sleep is registered with a sleep diary as subjective measurement. The adolescents fill out the sleep diary for five school nights and two weekend nights, keeping track of lights out, sleep onset, sleep offset and getup via an ecological momentary assessment app m-Path.[41] TST, SOL, SE, and NoA are calculated analogous to the actigraph data.

**Sleep problems.** Sleep problems are measured using two self-report and one parent-reported questionnaire. The following two subscales of the School Sleep Habits Survey are used: Sleepiness and sleep/wake problem behaviors.[42] This is a validated self-report questionnaire with acceptable internal consistency (sleepiness;  $\alpha = .70$ ; sleep/wake problem behaviors;  $\alpha = .75$ ).[43] To measure sleep deprivation, the Chronic Sleep Reduction Questionnaire is used (CSRQ).[44] This self-report questionnaire is validated, and has good internal consistency ( $\alpha = .85$  in clinical and  $\alpha = .87$  in control sample).[45] Children Sleep Habits Questionnaire (CSHQ) is used to gain insight in parents' perception of their children's sleep.[46] This is a validated, parent-report questionnaire with acceptable internal consistency ( $\alpha = .78$  in clinical and  $\alpha = .68$  in control sample) and acceptable test-retest reliability (.62 - .79).[46]

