### **Secondary outcomes**

**ADHD symptoms.** Inattention and hyperactivity-impulsivity subscales of the Disruptive Behavior Disorder Rating Scale (DBDRS) are used to measure ADHD symptoms.[48] This parent-reported questionnaire is validated, and the internal consistency of the scales in a Flemish sample is good for inattention and hyperactivity-impulsivity.[48]

**Comorbidities.** Symptoms of multiple comorbidities are measured using self-, parent- and teacher-report questionnaires. The ODD subscale of the parent-reported DBDRS is used.[48] To evaluate symptoms of anxiety, the SCARED-R is administered.[49] The SCARED-R is a validated, self-report questionnaire with good psychometric properties.[50] The self-reported Child Depression Inventory 2 (CDI-2) is administered to assess depressive symptoms.[51] Again, this is a validated questionnaire with good internal consistency ( $\alpha = .88$ ).[51]

**Functional outcomes.** Parent-adolescent conflict is measured using the Conflict Behavior Questionnaire (CBQ).[52] This is a validated, parent-report questionnaire with acceptable to good internal consistency (appraisal of parent;  $\alpha = .73$ ; appraisal of dyad;  $\alpha = .89$ ).[53] To evaluate adolescents' educational achievement, parents complete the Homework Problems Checklist (HPC)[54] and teachers the Classroom Performance Scale (CPS).[55] Both questionnaires are validated and have an excellent internal consistency (HPC:  $\alpha$  ranging from .90 to .92; CPS: academic competence;  $\alpha = .98$ ; interpersonal competence;  $\alpha = .91$ ).

Additionally, exploratory at baseline two questionnaires are assessed as potential moderators; the self-rated Quick Delay Questionnaire (QDQ [58]) and the parent/guardian views on neuropsychological (dys)functioning of their adolescents (the Cognition And Motivation in Everyday Life; CAMEL [59]).

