### **Safety**

Recording of adverse events: The participant will be asked to report any adverse event related to the study-specific intervention to the study team. These reported events will be documented by the Investigator in the source documents.

The following minimum information should be recorded for each AR:

- AE description
- start and stop date of the AR
- severity
- seriousness
- causality assessment to the study interventions
- outcome

Reporting to the Ethics Committee

The sponsor will assess whether any relevant safety information that becomes available during the study should be reported ad hoc to the EC.

The sponsor has the obligation to, once a year throughout the clinical trial (or on request), submit a progress report to the EC containing an overview of all SARs occurred during the reporting period and taking into account all new available safety information received during the reporting period.

During the first two sessions of the intervention, participants can freely report any adverse event related to the study-specific intervention to their therapist. From the third session on the following question will be posed: "Has anything happened last week that was a danger to you? Like suicidal thoughts, risk-seeking for example bingedrinking, or anything like that.". We argue that posing this question best starts during the third session as during the first two sessions the main focus is on forming a relationship and building trust. However, asking this type of question is not a risk factor to elicit suicidal thoughts or behavior even in at-risk adolescents. Research shows that talking about suicide and idealization, reduces suicide and improves mental health (e.g. Dazzi et al., 2014).

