#### **Safety considerations**

Once a year throughout the clinical trial, a progress report is submitted to the Ethical Committee Research UZ/KU Leuven containing an overview of all serious adverse events (as defined by the Ethical Committee Research UZ/KU Leuven)[57] occurred during the reporting period and taking into account all new available safety information received during the reporting period. Adverse events will be recorded and systematically assessed during the sessions of the treatment. If adverse events are reported, these will be documented in a separate document by the therapists who provide the treatment and reported to the Ethical Committee Research UZ/KU Leuven, both directly after the report and annually in a summary. The following minimum information is recorded for each adverse event: 1) description, 2) start and stop, 3) severity and seriousness, 4) causality assessment to the study treatment, 5) outcome.

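### The only scripted adverse-event question asks about danger, so non-dangerous worsening during treatment enters the adverse-event record only by unscripted, self-attributed report, which falls short of the systematic assessment the plan claims

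*Combined protocol and SAP*

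**What the plan says.** The Safety section describes three routes by which an adverse event can come to light.

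- A general request: "The participant will be asked to report any adverse event related to the study-specific intervention to the study team". No wording, timing or form is given for it.
- Sessions 1 and 2, spontaneous report only: "During the first two sessions of the intervention, participants can freely report any adverse event related to the study-specific intervention to their therapist".
- Later sessions, one fixed question. The text says "From the third session on the following question will be posed", and the question is "Has anything happened last week that was a danger to you? Like suicidal thoughts, risk-seeking for example bingedrinking, or anything like that".

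The section then lists what must be recorded for each event, including severity, seriousness and a causality assessment. The Safety considerations section repeats a similar list and describes the procedure this way: "Adverse events will be recorded and systematically assessed during the sessions of the treatment".

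On the intervention, the plan states that "SIESTA consists of seven individual sessions with the adolescents, and two parental sessions". No adverse-event question to parents is described.

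Several non-dangerous problems appear elsewhere as efficacy outcomes. Under Primary outcomes: "The following two subscales of the School Sleep Habits Survey are used: Sleepiness and sleep/wake problem behaviors". Under Secondary outcomes: "The self-reported Child Depression Inventory 2 (CDI-2) is administered to assess depressive symptoms". Anxiety (SCARED-R, self-report) and parent-adolescent conflict (CBQ, parent report) are also secondary outcomes.

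**The concern.** A fixed question determines what a record can contain. An adolescent who has been sleepier by day, lower in mood, or arguing more at home about bedtime can truthfully answer no to a question about danger. That event is then recorded only if the adolescent raises it unprompted and has already connected it with the intervention. The second condition matters because the plan makes causality an item to be assessed for each recorded event. If the reporter screens on causality first, events wrongly thought unrelated never reach that assessment.

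What is at stake is the meaning of the adverse-event record and of the yearly progress report to the ethics committee. A short list could reflect few harms or a narrow question, and a reader told that assessment was systematic could not tell which. The participants are minors, and worsening that is not yet dangerous is what a therapist would want logged early.

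**Working it through.** The plan states no figure on this point, so the check is a comparison of its sections plus a simple count.

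**Step 1: coverage of the scripted prompt.** There are 7 adolescent sessions (Intervention and comparison) and the prompt starts at session 3 (Safety). Sessions covered: 7 − 2 = 5 of 7. With 46 participants per condition (Sample size estimates) and full attendance, that is at most 5 × 46 = 230 prompts, all in the SIESTA arm and all framed as danger. The 2 × 46 = 92 adolescent sessions before session 3 and the 2 × 46 = 92 parent sessions have no scripted prompt. None is described for the TAU arm, or for either arm between the end of treatment and follow-up.

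**Step 2: content of each route.**

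| Route | Scripted? | Limited to danger? | Limited to related events? |
|---|---|---|---|
| General request to participants | No | No | Yes |
| Sessions 1–2 | No | No | Yes |
| Sessions 3–7 | Yes | Yes | No |
| Parent sessions | None described | – | – |
| TAU arm | No scripted prompt | – | – |

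No row is both scripted and open to non-dangerous events whatever their cause. That combination is what the statement in Safety considerations would need.

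**Step 3: what the questionnaires add.** The section on where treatment is provided says that all questionnaires are completed at pre-test, post-test and follow-up. Ethics & procedure applies this to the paired TAU adolescent as well. Sleepiness, CDI-2, SCARED-R and CBQ are therefore available in both arms at three time points.

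**Step 4: what the questionnaires leave open.**

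- Statistical analysis specifies a mixed model with a time-by-condition interaction and effect sizes from change scores. These are mean comparisons, and an average improvement can hide a minority who worsen.
- No section says that worsening on a scale is reviewed, logged as an adverse event or reported.
- The planned time points fall before the first session, within about a week after the last, and three months later. Nothing is captured by these scales while treatment is under way.
- Scale scores carry no start date, stop date or causality assessment, which both safety sections require for each event.

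**Step 5: the two safety sections compared.** The Safety section has the sponsor decide whether information should be reported ad hoc, and the yearly report covers serious adverse reactions. Safety considerations has reported adverse events sent to the committee both at once and in a yearly summary, with the yearly report covering serious adverse events. The sections differ on which events go to the committee and when. This matters for any change that lengthens the list.

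**The case against.** The strongest reply is that these harms are measured, and measured better than a session log could. Validated scales for sleepiness, mood, anxiety and conflict are completed in both arms, and parents supply the conflict scale. A mean worsening relative to TAU can be detected with a proper comparator, which session reports from the SIESTA arm alone cannot offer. This stands. A reader might infer from the danger question that ordinary harms are never asked about in this trial, and the documents contradict that.

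The general request is also broader than danger, and the fixed question has an open ending. Both are fair. But the request has no script or schedule and covers only related events, and the open ending refers back to danger. How adolescents would actually answer is a judgement, not something the documents show.

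Session content gives therapists chances to hear of problems: the functional analysis in session 4, the sleep plan in sessions 5 and 6, and communication in the second parent session. That is true, but nothing instructs them to log what they hear as an adverse event.

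Two further inferences go too far. One is a numerical rate of missed events: the documents give no proportion of events that would be volunteered, so no rate can be derived. The other is that a thin adverse-event record would drive rollout: the Dissemination plan ties implementation to effectiveness and mentions no adverse-event rate.

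Finally, prompting adolescents enrolled for sleep problems will collect background complaints with no TAU rate beside them. Read literally, Safety considerations could also send each one straight to the ethics committee. Both are real costs, and the fix has to deal with them.

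**Conclusion.** The point holds in limited form. The described procedure does not support the claim of systematic assessment for non-dangerous events arising during treatment. The only scripted prompt is confined to danger and runs in 5 of 7 adolescent sessions in one arm. The other routes are unscripted and filtered by the participant's own view of cause, ahead of the plan's causality assessment.

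The gap concerns adverse-event elicitation and individual-level harm. It does not affect the efficacy analysis, and it does not leave the trial blind to average worsening in sleepiness, mood, anxiety or conflict. Its practical size cannot be quantified from the documents. The conclusion assumes that no adverse-event form or therapist instruction outside these documents supplies a broader prompt. If the therapist manual contains one, citing it in the Safety section would largely settle the matter of wording.

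**What to change.** 1. **Add an open question.** In the Safety section, place one cause-neutral question before the danger question, for example: *Is there anything new or worse since we last spoke, whatever the cause?* Leave the danger question unchanged. Put the same open question to parents in their two sessions.
2. **Remove the relatedness filter.** Ask for any new or worsened problem, record it, and only then assess severity, seriousness and causality.
3. **Reconcile the two safety sections.** State which events go to the ethics committee directly and which only in the yearly summary. Do this before the new question is used, so that minor complaints do not trigger immediate reports by default.
4. **Report individual worsening by arm.** In Statistical analysis, add the share of participants in each arm who worsen from pre-test on the sleepiness, CDI-2, SCARED-R and CBQ scales at post-test and follow-up. Fix the definition of worsening before allocation is known to the analysts. This supplies the missing comparator and needs no new data.
5. **List session-based events descriptively.** Show danger events and other events separately, and say plainly that there is no TAU counterpart.

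The cost is about a minute per session, a longer list of mostly minor and uncontrolled events, one added table, and a submission to the ethics committee. No extra visit, staff or instrument is needed. For waves already treated, the prompt cannot be applied in retrospect, but items 4 and 5 still can, and the claim of systematic assessment should be qualified in the report.

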### **Confidentiality**

In accordance with the Belgian law of 22 August 2002 on patient rights and the General Data Protection Regulation (or GDPR) (EU) 2016/679 of 27 April 2016 on the protection of individuals with regard to the processing of personal data and on the free movement of that data will respect participants privacy.

All information collected during this study will be pseudonymized. In the case of pseudonymisation, the key to these codes will only be accessible to the researchers. The key to pseudonymizing the data is deleted after all waves of the study. Only the coded data will be used in all documentation, reports or publications (in medical journals or congresses) about the study. Confidentiality of the data is therefore always guaranteed. The data controller is KU Leuven. The KU Leuven research team will have access to the personal data relevant to UZ Leuven's research (including questionnaire material, intelligence research, clinical psychological interviews). Limited information from the sleep interview, K-SADS and the results from the questionnaires HSDQ and MATE-Y collected at the first appointment (relevant for the intervention) will be fed back to the study psychologist involved. Furthermore, in the case of Serious Adverse Events (Serious Adverse Events) or a crisis situation, for example suicidality, (already involved) health professionals can be contacted by the researchers.

KU Leuven representatives, auditors, the Medical Ethics Committee and the competent authorities have direct access to your files to check the procedures of the study and / or the data, without violating confidentiality. This is only possible within the limits allowed by the relevant laws. By signing the consent form (parent(s)/guardian(s)/guardians) and the assent form (adolescents), after prior explanation, participants agree to this access.

Participants have the right to make a complaint about how their information is treated, with the KU Leuven and Belgian supervisory authority responsible for enforcing data protection legislation.

### **Statistical analysis**

The analyses are based on an intent-to-treat approach, whereby participants are analyzed as a function of the condition to which they had been assigned. A longitudinal linear mixed effects model will be applied, with the variance components error correlation structure among the repeated measures over pre-test, post-test, and follow-up. The model contains a random intercept varying over participants, a fixed effect of time (pre-test, post-test and follow-up), a random slope for time varying over participants, a fixed effect of condition (1 = SIESTA+TAU; 0 = TAU), and an interaction effect between time and condition. We will correct for multiple testing in the multilevel analyses. Additionally, the potential impact of COVID-19 restrictions is taken into account by including wave as a level in the multilevel analyses. Effect sizes (ESs) are computed by calculating the difference in change scores for SIESTA+TAU as compared to TAU only between post-treatment/follow-up and pre-test and dividing this amount by the pooled standard deviation of the change scores for SIESTA+TAU and TAU only. Confidence intervals for ESs are computed using procedures delineated by Odgaard and Fowler (2010).[56] Although participants are instructed to be off sleep medication and to not change their ADHD medication, they may not comply. Therefore, this is thoroughly assessed both at

post-test and follow-up. This allows for potential sensitivity analyses in the sleep medication free sample, and those that did not change ADHD medication.

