planning and organization. Therefore, our lab developed a CBT intervention that integrates sleep training with motivational interviewing, and planning/organizational skills with the aim of improving sleep problems in adolescents with ADHD.[24,25] The acronym is SIESTA [Sleep IntervEntion as Sympom Treatment for ADHD]. To tailor the intervention optimally towards the needs of adolescents with ADHD and enhance feasibility of the assessment and study protocol of our RCT, we piloted our SIESTA intervention and the study protocol in eight adolescents with ADHD and sleep problems.[26] Fine-tuning of the intervention and study protocol was based on the outcomes of the pilot study and feedback from adolescents with ADHD and parents from focus groups.

[figure not shown]
The objective of this study is to test the effectiveness of SIESTA in combination with treatment as usual (TAU) for ADHD symptomatology compared to TAU only in a randomized controlled trial. SIESTA is expected to improve sleep architecture measured both objectively and subjectively; specified as total sleep time (TST), sleep onset latency (SOL), sleep efficiency (SE), and number of awakenings (NoA), sleep problems and sleep hygiene practices (primary outcomes). Regarding secondary outcomes SIESTA is expected to improve ADHD symptoms, comorbid symptoms and functional outcomes. Both primary and secondary outcomes are expected to show greater improvement in the SIESTA group, both on the short (post-test) and middle long term (approximately three months follow-up), than in the TAU only group.

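### The random slope and variance-components structure in the primary mixed model are poorly matched to the separate post-test and follow-up effects it has to test

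*Combined protocol and SAP*

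**What the plan says.** The Statistical analysis section is the only description of the primary model. It states: "The model contains a random intercept varying over participants", then "a fixed effect of time (pre-test, post-test and follow-up), a random slope for time varying over participants", condition, and "an interaction effect between time and condition", fitted "with the variance components error correlation structure among the repeated measures over pre-test, post-test, and follow-up". Wave is added as a further level.

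The Introduction expects greater improvement with SIESTA "both on the short (post-test) and middle long term (approximately three months follow-up), than in the TAU only group". The effect-size definition also treats the two occasions separately: "Effect sizes (ESs) are computed by calculating the difference in change scores for SIESTA+TAU as compared to TAU only between post-treatment/follow-up and pre-test".

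For the sleep measures, Primary outcomes says "Participants wear an actigraph for five school nights and two weekend nights" and "The adolescents fill out the sleep diary for five school nights and two weekend nights". It does not say whether the seven nights are averaged before modelling. The questionnaire outcomes have one value per occasion.

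Five things are not stated:
- whether time is a factor or a number in the fixed part;
- how time is coded in the random slope;
- whether variance components governs the residuals, the random effects or both;
- which contrasts test the hypotheses;
- what is done if the fit fails.

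**The concern.** Three occasions with one value each carry little information on covariance: three variances and three covariances. A random intercept, random slopes and a residual variance can ask for more than that. The simplified versions that remain estimable work by restricting the covariance. The standard error of each change-score contrast depends directly on that covariance, so a wrong restriction gives wrong error bars at post-test or follow-up.

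Non-identifiability does not in itself bias the contrasts, because they depend only on the total covariance. The harm is practical. The fit may be refused or fail to converge, no fallback is named, and the primary model would then be settled after the data are seen.

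**Working it through.** The plan gives no figure of its own to reproduce here. Its sample-size figures do not enter, apart from the total of 92 used in the simulation below. The correlations and visit months are assumptions. Ethics & procedure puts post-test within a week of the last session and follow-up after 3 months, but treatment length in weeks is not given.

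**1. Identifiability.** The model implies V = Z G Z' + R. V is 3x3 with 6 distinct elements. Counting covariance parameters against the rank of their mapping to V:

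| Random part, one value per occasion | Parameters | Rank |
|---|---|---|
| Factor slope, full G, one residual variance | 7 | 6 |
| Factor slope, one common variance, one residual variance | 3 | 2 |
| Factor slope, diagonal G, three residual variances | 6 | 4 |
| Factor slope as dummies, diagonal G, one residual variance | 4 | 4 |
| Linear slope, diagonal G, one residual variance | 3 | 3 |
| Linear slope, full G, one residual variance | 4 | 4 |
| Linear slope, full G, three residual variances | 6 | 6 |

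The first three rows are not identifiable. In the first, Z is invertible, so any small enough residual variance can be paired with a G that gives the same V. In the second, only the sum of slope and residual variance is visible. If all seven nightly values per occasion are modelled, the full factor slope is identified (7 parameters, rank 7).

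**2. Error rate of the fittable versions.** Assume unit variances and correlations pre-post .5, pre-follow-up .3, post-follow-up .6. The true contrast variances are 2(1 - .3) = 1.40 at follow-up and 2(1 - .5) = 1.00 at post-test. Each restricted V is the one closest to the true covariance in Gaussian divergence. The large-sample type I error is 2[1 - Phi(1.96 x sqrt(model variance / true variance))].

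- Independent dummy slopes. All covariances are forced equal, at .468, with pre-test and follow-up variances .985 and 1.033. Follow-up variance: .985 + 1.033 - 2(.468) = 1.082. Then 1.96 x sqrt(1.082/1.40) = 1.72, and the error is 8.5%. Post-test: 1.033 against 1.00, error 4.6%.
- Independent intercept and linear slope, equal spacing. Follow-up: .896 + 1.212 - 2(.455) = 1.198, error 7.0%. Post-test: .961, error 5.5%.
- Correlated intercept and linear slope, equal spacing. Follow-up: 1.40, error 5.0%. Post-test: .90, error 6.3%.

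The same calculation for other assumed patterns (equal spacing; follow-up error / post-test error, in %):

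| Pre-post / pre-follow-up / post-follow-up | Independent dummies | Independent linear | Correlated linear |
|---|---|---|---|
| .5/.5/.5 | 5.0 / 5.0 | 5.0 / 5.0 | 5.0 / 5.0 |
| .6/.5/.6 | 6.5 / 4.6 | 6.0 / 4.6 | 5.0 / 5.0 |
| .5/.4/.6 | 7.4 / 5.0 | 6.1 / 5.8 | 5.0 / 6.3 |
| .6/.4/.6 | 7.8 / 4.3 | 6.8 / 4.3 | 5.0 / 5.0 |
| .4/.3/.6 | 7.8 / 5.7 | 6.3 / 6.7 | 5.0 / 7.4 |
| .6/.4/.7 | 9.2 / 4.6 | 6.9 / 6.0 | 5.0 / 6.7 |

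**3. Point estimates.** In 150 simulated trials of 92 participants with a sustained effect of 0.60 SD, categorical fixed time with a correlated linear random slope gave a mean post-test estimate of 0.60. This equalled the raw difference in change scores to rounding error. Its mean standard error was 0.229, against a true 0.219 under the covariance simulated.

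**4. Linear fixed time, for completeness.** For a sustained effect d = (0, 1, 1), the fitted slope is sum[(t - mean t)d] / sum[(t - mean t)^2], and the reported post-test effect is the slope times the post-test time.
- Times 0/1/2: 1/2 x 1 = 0.50.
- Months 0/2/5: 2.333/12.667 x 2 = 0.37.
- Months 0/4/7: 3.667/24.667 x 4 = 0.59.

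The simulation gave 0.29 against a true 0.60.

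**The case against.** A workable model fits the sentence. The fixed effect is listed as three named occasions, and the random slope is mentioned separately. Categorical fixed time with a linear random slope is therefore a natural reading. It is identifiable, and a linear random slope constrains only the covariance, not the complete-data point estimate. If variance components also means a separate error variance at each occasion, a correlated linear slope has 6 parameters and rank 6. For the .5/.3/.6 pattern it reproduces the true covariance exactly. All of this stands.

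A reader might infer that the planned model cannot deliver a post-test effect at all, or that it halves it. The documents do not support either. The halving needs a linear fixed time effect, which is stated nowhere and which the Introduction and the effect-size definition make unlikely.

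It is also fair that the documents give no correlations, so the size of the inflation depends on the patterns assumed, and that one value per occasion is certain only for the questionnaires.

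What does not stand is that the matter is merely one of detail. The structure the plan names is variance components. When that is applied to the random effects, the fittable versions restrict the covariance and inflate follow-up error in every unequal pattern above. The readings that perform well need choices the plan does not make.

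**Conclusion.** The concern holds as a mismatch between the stated covariance model and its two target effects. With one value per occasion (questionnaires, and actigraphy or diary if nights are averaged), a three-category random slope with full covariance or one common variance is not identifiable.

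The fittable variance-components versions give follow-up type I error of about 8.5% (independent dummies) or 7% (independent intercept and linear slope) at the assumed .5/.3/.6. Across the other unequal patterns it is about 6-8.5%, apart from 9.2% for dummies at .6/.4/.7. It is 5% if all correlations are equal. A correlated linear slope with one residual variance keeps follow-up near 5%, but post-test error can be about 5-8%.

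These are large-sample figures. They assume equal true variances and a pre-test to follow-up correlation that is the lowest of the three in every unequal pattern. Only under linear fixed time, an unlikely reading, would a sustained effect appear at post-test as about 0.4-0.6 of its true size, with visit spacing assumed.

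**What to change.** For outcomes with one value per participant per occasion:
- Replace the random intercept, random slope and variance-components structure with a REML repeated-measures model with time as a three-level factor, condition and their interaction, and an unstructured 3x3 within-participant covariance.
- Name the post-test and follow-up time-by-condition contrasts as the tests of the hypotheses in the Introduction.
- Keep wave in the model, as planned.
- State that actigraphy and diary nights are averaged per occasion. If nights are to be modelled singly, keep participant and occasion random effects for those outcomes.
- Name a fallback in advance in case the model does not converge.

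The cost is wording only. The unstructured matrix needs 6 covariance parameters instead of 3 or 4, which 92 participants support easily. It leaves the visit schedule, the data collected and the sample size unchanged.
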